LIST OF ABBREVIATIONS

Abbreviation	Explanation
AI	Artificial Intelligence
AUROC	Area Under the Receiver Operating Characteristic
BSI	British Standards Institution
CI	Chief Investigator
CONSORT	Consolidated Standards of Reporting Trials
DCS	Department of Computer Science
EPR	Electronic Patient Record
GCP	Good Clinical Practice
H&E	Haematoxylin and Eosin
HRA	Health Research Authority
IRAS	Integrated Research Application System
iQC	Image Quality Control
ISRCTN	International Standard Randomised Controlled Trial Number
IVD-CE	In Vitro Diagnostic - Conformité Européene (European Conformity)
MHRA	Medicines and Healthcare products Regulatory Agency
MRC	Medical Research Council
NPV	Negative Predictive Value
PI	Principal Investigator
PPI	Patient & Public Involvement
PPV	Positive Predictive Value
REC	Research Ethics Committee
R&D	Research and Development
SMG	Study Management Group
SOP	Standard Operating Procedure
SSC	Study Steering Committee
TIA	Tissue Image Analytics
UHCW	University Hospital Coventry and Warwickshire
UK-CA	United Kingdom Conformity Assessed
UoW	University of Warwick
WCTU	Warwick Clinical Trials Unit
WSI	Whole-Slide Image

GLOSSARY

Term	Definition
Case	The whole case belonging to a patient, this may contain one or more specimens.
Specimen	A piece of tissue taken from specific part of the large bowel. The separate specimens taken from that patient form the case (e.g., often multiple biopsies are taken from different parts of the colon in a single case). The terms sample, specimen and biopsy all mean the same thing.
Slide	The specific slides produced from each specimen/specimens. Each specimen may be split into/ produce several slides (for example large specimens or if a pathologist has requested multiple levels), or multiple specimens may be placed on a single slide. The diagnosis of a specimen issued in the clinical report at each trust.
Reference diagnosis	The study pathologist's diagnosis at time of recruitment. This is considered the gold standard for algorithm comparison.
COBix diagnosis	The diagnosis given by COBix.
Ground truth diagnosis	The final diagnosis given to cases where there was discrepancy between the reference diagnosis and COBix diagnosis, following consensus review of the case.

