4.3 Medical device classification

COBix is intended to recognise large bowel biopsies as normal or abnormal. It is intended that recognition of normal cases will generate an automated report. This report is designed to be posted onto the electronic patient record (EPR) and communicated to the patient, potentially using the NHS app on mobile devices. It is intended that abnormal cases will remain in the pathologist reporting workflow with annotations visible to the pathologist identifying the regions of interest (ROI) recorded as abnormal. COBix will be classified as a class IIb device under Regulation (EU) 2017/745 Rule 11.

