4.5 Study size, case selection and case enrolment

The study will enrol 11,000 cases. Sample size for the analysis corresponds to the number of specimens and on average, it is expected that each case will have three specimens. In assessing sample size adequacy, we were conservative assuming that there will be one specimen per case, rather than the expected average of three per case. A sample size of 11,000 is adequate to estimate diagnostic measures (sensitivity, specificity, negative predictive value (NPV) and positive predictive value (PPV)) with high precision if the study will have a positive finding of obtaining sensitivity and NPV values of at least 0.98. Assuming we will observe NPV=0.98 and same number of normal cases by pathologists and COBix algorithm, varying prevalence between 49% and 90% (observed data in seven sites in Table 1), the largest margin of error (1.96 x standard error) for any of the four diagnostic measures is 0.02 so that confidence intervals for all diagnostic measures will be very narrow. This sample size may seem large, but it is essential to deliver comprehensive assessment of the tool across all patient groups and the full range of pathological entities encountered in practice.

The study has been designed with the majority of cases (9,900) coming from retrospective cases, with 1,100 cases being recruited prospectively. Using retrospective cases is appropriate in this setting and ensures the volume of cases can be recruited and examined in the time available. It also ensures rare and unusual entities can be included so we can explore how these are handled by the algorithm. Prospectively recruited cases will be selected sequentially and will allow the study to collect health economics data, including the time taken for pathologists to examine normal biopsies and the broader impact on pathology workflow.

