- 5) **Neoplastic urgent** (any neoplastic lesion which includes either high grade dysplasia or invasive carcinoma or other malignant diagnosis)

These categories match then the classification tree in figure 4.

All H&E slides from a case will be seen by the algorithm, but diagnostic categorisation will be done at the specimen level within a case.

[figure not shown]

Figure 4 is a schematic diagram of the COBIx biopsy classification tree depicting how specimens will be classified in the study.

Both pathologists and COBIx classifies each specimen enrolled into one of the five diagnostic categories shown.

Case selection

Each site collects 1000 cases for the study in the following manner:

First, a search of the pathology archive for any of the diagnoses of interest (Cases of interest) listed below of any age and as many of these cases as can be found number X.

Second, a series of cases 900-X from any time period prior to August 2023 using an enrichment process to ensure 30% of cases come from minority ethnic groups, remaining cases are collected sequentially.

Third, a series of 100 cases collected during the trial period to be arranged with the coordinating centre.

Cases of interest, and other interesting and educational cases discovered during the course of the study, will be configured into a training set for the RCPATH Portal.

For the cases enrolled into this study the site will review and ascertain the diagnosis of each specimen and categorise this into one of the 5 categories using the definitions provided.

This work is to be supervised by the principal investigator for the site, the work may be delegate to other staff (trainee pathologists, biomedical scientists, medical students etc. providing they have sufficient training and knowledge and are adequately supervised in this work) as appropriate.

Inclusion criteria

Large bowel endoscopic biopsies from adult patients (over 18 years)

Exclusion criteria

Specimens which are not from large bowel endoscopic biopsies

Incomplete cases with lost slides

Cases from person opting out via the NHS Data opt-out scheme

Faded or damaged slides

Incomplete or missing meta data

The following metadata is required for each case:

Site code

Laboratory number

Ethnic group

Gender

Age group

Procedure type

Tissue Type

Date of biopsy

Colonoscopy report

Clinical details

Specimen parts

Specimen blocks

Macroscopic report

Microscopic report

Diagnosis

SNOMED Code

Scanner type

Image resolution

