4.9 Outcome measures

The study measure is categorisation of diagnosis of a specimen into either normal or abnormal and, secondarily for abnormal specimens, into one of the four abnormal categories listed above. Reference diagnosis category by site pathologists (gold standard) will be compared to COBix algorithm diagnosis category (experimental/intervention) using the following study outcomes.

Primary outcomes: For the validation part of the study, using a pre-specified COBix algorithm threshold, the outcomes will be sensitivity, specificity, negative predictive value (NPV) and positive predictive value (PPV) to detect normal versus abnormal (all categories other than normal including changes of uncertain significance). For all possible COBix algorithm thresholds, the outcomes will be receiver operating characteristic (ROC) and precision-recall (PR) curves.

Secondary outcomes: Agreement on abnormal categories, neoplastic versus non- neoplastic.

Tertiary outcomes: Agreement on urgent versus non-urgent categories (invasive carcinoma and or high-grade dysplasia versus non-invasive neoplasia, and acute inflammation, necrosis, ulceration versus all other pathology).

Additionally, we will use items recorded in clinical details and /or endoscopic findings to reduce the possibility and impact of false negative results from the COBix algorithm and to development the safest possible reporting pathway in practice.

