6. STATISTICAL ANALYSIS

The aim of the study is to validate the COBix diagnostic tool that will be developed before the study begins. We will compute diagnostic measures of sensitivity, specificity, positive predictive value (PPV) and negative predictive value (NPV). The gold standard in the analysis is a pathologist's reference diagnosis. A positive result will be the ability of the COBix diagnostic tool to screen out normal cases. For patient safety, the desire is for the tool to achieve this whilst minimising false negatives and so very high sensitivity and very high NPV are desired. NPV is a function of prevalence of abnormal cases. The prevalence in the study will not be representative because there will be enriching for rare cases (e.g., by ethnicity). However, very high NPV is desired for any case mix. COBix will be considered a good tool if sensitivity and NPV are above 0.98. Specificity will quantify the proportion of normal cases that are screened out and hence the saving in pathologists' workload.

For the cases that are abnormal on both the COBix algorithm and reference diagnosis, based on the categorisation "neoplastic" and "non-neoplastic", we will compute kappa statistic. We will use the kappa statistic to assess agreement between COBix and pathologist diagnosis in categorising abnormal cases as neoplastic or non-neoplastic. Also, taking the gold standard as a pathologist's categorisation of an abnormal case as neoplastic or non-neoplastic, we will compute sensitivity, specificity, and other diagnostic measures.

For the cases that are abnormal on both the COBix algorithm and reference diagnosis, based on the categorisation "urgent" and "non-urgent", we will compute kappa statistic. We will use this kappa statistic to assess agreement between COBix and pathologist diagnosis in categorising an abnormal case as urgent or non-urgent. Also, taking a pathologist's reference diagnoses as the gold standard, we will compute sensitivity, specificity, and other diagnostic measures. Comparison of categorisation as urgent and non-urgent will be based on all abnormal cases and in subgroup analyses of separately analysing neoplastic cases and non-neoplastic cases.

Subgroup analysis will repeat the above set of analyses for clinically important patient subgroups such as categories based on sex, ethnicity, age and site of the biopsy.

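### Accuracy is measured per specimen, but specificity is read as the share of normal cases screened out, and the protocol does not settle whether release is by specimen or by case

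*Protocol*

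**What the plan says.** The glossary separates the two units. A case is "The whole case belonging to a patient, this may contain one or more specimens", while a specimen is one piece of tissue from one part of the bowel, and biopsy is declared a synonym of specimen.

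The measurement unit is the specimen throughout:
- Section 4.5, on study size: "Sample size for the analysis corresponds to the number of specimens and on average, it is expected that each case will have three specimens".
- Section 4.5, on classification: "diagnostic categorisation will be done at the specimen level within a case".
- Section 4.9, on outcomes: "The study measure is categorisation of diagnosis of a specimen into either normal or abnormal".

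The interpretation is worded per case. Section 6 describes a positive result as the tool's ability to screen out normal cases, and adds that "Specificity will quantify the proportion of normal cases that are screened out and hence the saving in" pathologists' workload. The same section requires sensitivity and NPV above 0.98 and provides for a futility stop on sensitivity or NPV. Neither rule names its unit.

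The release unit differs between sections. The text under Figure 1 in Section 4.2 attaches the automated report to biopsies called normal and says that those specimens would not go to the pathologist. Section 4.3 says "It is intended that recognition of normal cases will generate an automated report" and keeps abnormal cases in the reporting workflow. The protocol gives no rule for combining specimen results into a case result and names no case-level accuracy measure.

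**The concern.** Under case-level release, a case leaves the pathologist's list only when every one of its specimens is called normal. One false positive among three normal specimens keeps the whole case there. A specimen called normal within a mixed case also stays with a case that the pathologist still has to handle. Specimen specificity is then not the quantity that Section 6 says it is.

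The safety reading has the same gap. The automated report in Section 4.3 concerns a patient's case, while the NPV that supports it is per specimen. The protocol already fixes the success limit at 0.98, so the unit is not a detail of analysis: it can decide whether the tool meets the limit.

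**Working it through.** **Inputs from the protocol.** 11,000 cases, 11 sites, about three specimens per case (about 33,000 in all); planning NPV 0.98 with equal numbers called normal by pathologist and algorithm; prevalence of abnormality 49% to 90%; largest stated margin 0.02 (Section 4.5). Overall normal share 34.5% (Table 1).

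**Assumptions, not in the protocol.** Exactly three specimens per case; 34.5% used as the specimen-level normal share; within-patient correlation of errors from 0 to 1; within-patient correlation of true status from 0 to 0.9, modelled as beta-binomial.

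**1. The plan's own precision figure.** Equal numbers called normal with NPV 0.98 imply specificity 0.98. At 90% prevalence the 11,000 basis has 1,100 normals, so the margin is 1.96 × √(0.98 × 0.02 / 1,100) = 0.0083. The stated 0.02 is not reproduced; it is wider than the calculation gives.

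**2. Case specificity.** For an all-normal case of three specimens with independent errors, case specificity = (specimen specificity)³. With fully correlated errors it equals specimen specificity.

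| Specimen specificity | Independent errors | Fully correlated errors |
|---|---|---|
| 0.98 (implied by planning) | 0.98³ = 0.941 | 0.98 |
| 0.90 (illustrative) | 0.90³ = 0.729 | 0.90 |

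**3. Normal specimens in mixed cases.** The share of normal specimens that lie in wholly normal cases is P(all three normal) / 0.345.

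| Correlation of true status | P(all three normal) | Share of normal specimens in all-normal cases |
|---|---|---|
| 0 | 0.345³ = 0.041 | 12% |
| 0.3 | 0.121 | 35% |
| 0.6 | 0.213 | 62% |
| 0.9 | 0.311 | 90% |

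Under case-level release the remaining normal specimens stay in the workflow even when correctly called.

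**4. Case NPV.** With prevalence 65.5%, specimen sensitivity is 1 − 0.02 × 0.345 / 0.655 = 0.9895, so an abnormal specimen is called normal with probability 0.0105. A case is called normal if all three specimens are. With P(k) the probability of k truly normal specimens and errors independent given true status:

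case NPV = P(3) × 0.98³ / Σ P(k) × 0.98^k × 0.0105^(3−k)

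- Correlation 0: P(3) = 0.0411 and P(2) = 0.2339. The numerator is 0.0387 and the denominator 0.0411, so case NPV is 0.941.
- Correlation 0.3: P(3) = 0.1209 and P(2) = 0.1977. The numerator is 0.1138 and the denominator 0.1158, so case NPV is 0.982.
- Correlation 0.6 and 0.9: case NPV is 0.994 and 0.999.

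In simulation, an error correlation of 0.5 in place of independence changes these little (0.947, 0.985, 0.994, 0.998). Case sensitivity, where any flagged specimen keeps the case, is 0.9975 or more against 0.9895 per specimen.

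**5. Can the verdict depend on the unit?** Yes, both ways. A specimen NPV just above 0.98 goes with a case NPV of about 0.94 if specimens are independent. Conversely, with specimen specificity 0.80 and true-status correlation 0.6, simulation gives specimen NPV 0.976 (below the limit) and case NPV 0.992 (above it).

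**The case against.** The strongest reply is that Section 4.9 fixes the specimen as the outcome unit and that Section 6 uses the word cases loosely. If release is by specimen, as Section 4.2 reads, specimen specificity does measure the normal specimens removed. That stands, and it makes the overstatement conditional on the release unit. It does not remove the conflict with Section 4.3.

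Section 7 also bears on workload. For prospective cases it times each slide, the whole of each normal case, and the normal slides of mixed cases separately. So workload is not judged from specificity alone. This lessens the point, but it covers only the 1,100 prospective cases and supplies no case-level accuracy.

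Three stronger readings are tempting, and the protocol does not support them.

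- *A reader might infer that the planned intervals are too narrow.* The protocol specifies no interval method that treats 33,000 specimens as independent, and the method may properly sit in the SAP. Planning counts one specimen per case. With three per case the within-patient design effect is at most 1 + 2 × 1 = 3, and 33,000 / 3 = 11,000, exactly the planning number. The stated 0.02 also exceeds the 0.0083 computed above. Only if specimens were analysed as independent would intervals be too narrow, by a factor of √1.2 = 1.10 to √3 = 1.73 for within-patient correlation 0.1 to 1.
- *A reader might cube 0.98 and infer that about 6% of fully auto-reported cases hide an abnormality.* That holds only if specimens from one patient are independent. Cases with all specimens called normal are a selected group, and case NPV rises above 0.98 once true status correlates within patient.
- *A reader might ask for case-level co-primary outcomes.* That changes the primary outcome set and is more than the problem needs.

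**Conclusion.** The point holds in a limited form. The protocol measures accuracy per specimen, interprets specificity per case, and gives two different release units. If release is by case, the workload reading in Section 6 is too favourable: about 0.94 instead of 0.98 at the planning assumptions with independent errors, and 0.73 to 0.90 for an illustrative specimen specificity of 0.90. Normal specimens in mixed cases are a further loss. If release is by specimen, specificity is a fair measure of specimens removed, but still not of normal cases screened out.

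For NPV the conclusion is only that the two units differ, in either direction (about 0.94 to 0.999 for specimen NPV 0.98). The 0.98 rule therefore needs a stated unit. The sizes rest on three specimens in every case, a 34.5% normal share among specimens, and correlations that the protocol does not give. The enriched study sample may differ on all of these. The point should be corrected before analysis; it does not call the design or the sample size into question.

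**What to change.** - Reconcile Sections 4.2, 4.3 and 6 on whether release is by specimen or by case.
- State in Section 6 that the 0.98 rule and the futility rule apply per specimen, in line with Section 4.9.
- Add supporting case-level sensitivity, specificity and NPV, with a case counted as normal only if every specimen is normal, for both the reference and the algorithm.
- Take any statement about normal cases screened out, or case workload saved, from the case-level result.
- Where specimens are the unit, compute intervals with a method that allows for clustering by case and site.

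The cost is wording and a little more analysis. Section 4.5 already assigns each slide a case number and a part identifier, so no new data are needed. The downside is that the reported case-level workload saving may be less favourable than the specimen figure.

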4.2 The COBix Algorithm Version 1.0

[figure not shown]

Figure 1 Overview of the COBix algorithm for large bowel endoscopic biopsies.

Scanned WSIs of the biopsies are pre-screened by the COBix algorithm which divides the biopsies into normal and abnormal outcome baskets. Abnormal biopsies are triaged into urgent and non-urgent groups depending on the pathology identified. Biopsies with a normal result trigger an automated report of normal tissue. These specimens would not be examined by the pathologist except at the request of the clinician or for quality assurance purposes.

The COBix algorithm (Figure 1) is an in-vitro diagnostic medical device (computer software), intended for use on endoscopic large bowel biopsies from adult patients (over 18 years old) to screen normal from abnormal biopsies and assist in the triage of cases with serious disease for urgent pathologist review. Screening for normal is intended to provide a means of automated reporting of these specimens.

COBix combines two parallel strands of AI technology: **(a)** Hover-Net, the state-of-the-art deep learning model providing individual cell recognition^{11,12}, and **(b)** iterative-draw-and-rank-sampling (IDARS) algorithm, a weakly supervised deep learning strategy recently published in The Lancet Digital Health¹³, for the detection of colorectal carcinoma from routine H&E slides. Combining these algorithms predicts normal and the presence of neoplastic disease, invasive carcinoma and areas of acute inflammation and confidence levels for these predictions. The tool operates on digitised WSIs of colon biopsy slides stained with H&E.

[figure not shown]
[figure not shown]
A**B**

Figure 2 Results of the COBI algorithm based on IDARS a weakly supervised algorithm developed from slide deep learning of data with just the slide level diagnosis.

As shown in Figure 2A, there is excellent detection of neoplastic lesions by the algorithm, but detection of inflammatory conditions is less strong. Figure 2B shows the H&E image of a hyperplastic polyp with a corresponding heat map of the abnormality detected by the algorithm. (IDARS stands for iterative draw and rank sampling which is the approach taken to select informative patches in the training sets used in the algorithm development).

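### Neoplastic and urgent sensitivity read as limited to specimens COBix also called abnormal, so no defined measure gives the rate at which each category is called normal

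*Protocol*

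**What the plan says.** Protocol section 4.9 makes the normal/abnormal split the primary outcome, with sensitivity, specificity, NPV and PPV. The categories come "secondarily for abnormal specimens, into one of the four abnormal categories listed above". It does not say whether abnormal is judged by the pathologist, by COBix or by both.

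Section 6 has one paragraph for neoplastic versus non-neoplastic and one for urgent versus non-urgent. Each begins "For the cases that are abnormal on both the COBix algorithm and reference diagnosis" and attaches that set to kappa. Each then adds that, with the pathologist as gold standard, "we will compute sensitivity, specificity, and other diagnostic measures". No separate denominator is given for these. The urgent paragraph ends: "Comparison of categorisation as urgent and non-urgent will be based on all abnormal cases", with separate analyses of neoplastic and non-neoplastic cases as subgroups.

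The success criterion is on the pooled split only: "COBix will be considered a good tool if sensitivity and NPV are above 0.98". On intended use, section 4.2 says that a normal result produces an automated report and that "These specimens would not be examined by the pathologist except at the request of the clinician" or for quality assurance.

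**The concern.** If the both-abnormal set governs sensitivity as well as kappa, a carcinoma or an ulcerated colitis that COBix calls normal is not a miss in the neoplastic or urgent analysis. It is removed from the denominator. The category figures would then describe how well COBix sorts specimens it has already flagged, while a reader would take them as the proportion of urgent or neoplastic specimens the tool finds.

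The primary sensitivity does not fill the gap. It gives a missed cancer the same weight as a missed minor abnormality, and a small category can do badly while the pool still does well. The subgroups that section 6 names are sex, ethnicity, age and site of biopsy; reference category is not among them. Because a normal call would normally end pathologist review, the rate at which each urgent category is called normal is a central safety figure for the triage claim, and no outcome clearly delivers it.

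**Working it through.** **1. Which denominator the text supports**

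- For kappa, the both-abnormal set is explicit.
- For sensitivity and specificity it is inferred. They follow in the same paragraph, no other set is named, and the labels are two-way, so a COBix normal has no cell and no rule.
- For the urgent comparison, the reference to all abnormal cases can mean the whole both-abnormal set as opposed to its two subgroups, or all reference-abnormal cases. The text does not settle it.

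**2. The plan's own precision figure**

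Section 4.5 gives a largest margin of error of 0.02 for the four primary measures. With NPV 0.98 and 90% prevalence there are 1,100 normals, and 1.96 × √(0.98 × 0.02 / 1,100) = 0.0083. So 0.02 is a loose upper bound and the claim of adequate precision stands. It concerns the primary measures only; the protocol gives no figure for the categories.

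**3. How many specimens would be excluded**

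Inputs: 11,000 specimens (section 4.5, one per case); prevalence of abnormal 49% to 90% (section 4.5); 65.5% abnormal from the 34.5% normal in Table 1; pooled sensitivity at its limit of 0.98.

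Excluded = 11,000 × prevalence × 0.02:

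- 49%: 5,390 × 0.02 = 108
- 65.5%: 7,205 × 0.02 = 144
- 90%: 9,900 × 0.02 = 198

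With the expected 33,000 specimens these counts triple (432 at 65.5%). How many of them are neoplastic or urgent is unknown.

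The NPV part of the criterion tightens this. Under the protocol's planning assumption of equal numbers of normals by COBix and pathologist, NPV 0.98 means false negatives = 0.02 × normals: 112 at 49% (so the sensitivity limit of 108 binds), 0.02 × 3,795 = 76 at 65.5%, and 0.02 × 1,100 = 22 at 90%.

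**4. Effect on a category's sensitivity**

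Let m be the share of the category that COBix calls normal. Then

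all-reference-positive sensitivity = both-abnormal sensitivity × (1 − m).

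With an assumed both-abnormal sensitivity of 0.98:

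- m = 2%: 0.98 × 0.98 = 0.960
- m = 5%: 0.931
- m = 10%: 0.882
- m = 20%: 0.784

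The reported both-abnormal value is 0.98 in every row.

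**5. What the pooled criterion could hide**

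This is a worst case at 65.5% prevalence: all false negatives fall in one category. The category shares are assumed, as the protocol gives none, and the both-abnormal sensitivity is again taken as 0.98.

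| Share of abnormals | Category size | m with 144 misses | Sensitivity | m with 76 misses (NPV also 0.98) | Sensitivity |
|---|---|---|---|---|---|
| 5% | 360 | 40% | 0.588 | 21.1% | 0.774 |
| 10% | 720 | 20% | 0.784 | 10.5% | 0.877 |
| 20% | 1,441 | 10% | 0.882 | 5.3% | 0.928 |
| 30% | 2,162 | 6.7% | 0.915 | 3.5% | 0.946 |

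These are bounds, not forecasts. If misses are spread evenly at 2%, 0.98 falls only to 0.960.

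**The case against.** The strongest reply is that a missed cancer is already caught. The primary outcomes are measures "to detect normal versus abnormal (all categories other than normal including changes of uncertain significance"), so such a specimen is a false negative there and lowers both sensitivity and NPV. Section 6 gives that measure the patient-safety role, and section 4.7 sends every discrepant specimen to at least three pathologists. This stands. A reader might infer that cancers called normal escape the analysis altogether; the documents do not support that. What is missing is their rate by category.

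Second, the restriction is written for kappa, and the wording on sensitivity, which takes the pathologist's diagnosis as gold standard, could be meant to apply to all reference-abnormal specimens. This also stands in part: it is too strong to say that the protocol expressly restricts sensitivity. But nothing states the wider set or says how a COBix normal would count in it.

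Third, COBix works in two stages, and performance among specimens that reach the second stage is a legitimate quantity. Agreed. It misleads only if read as sensitivity of the whole pathway, and nothing in section 6 labels it otherwise.

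Fourth, the statistical analysis plan, not seen here, may define the denominators. It may. The point rests on an analysis set that the protocol itself states and that a plan following it would inherit.

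Finally, the remark in section 4.2, "but detection of inflammatory conditions is less strong", may tempt a reader to conclude that COBix misses urgent inflammation. It describes the earlier COBI algorithm based on IDARS; section 4.1 says COBix was introduced to improve on non-neoplastic disease. It is not evidence about the device under test.

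**Conclusion.** The point holds in a limited form. On the natural reading of section 6, neoplastic and urgent sensitivity are conditional on COBix having called the specimen abnormal, explicitly so for kappa and by inference for sensitivity, with the urgent analysis ambiguous. As measures of the whole pathway they are too high whenever any specimen in the category is called normal, and the pooled primary measures cannot supply the category-specific rate.

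At pooled sensitivity 0.98 about 108 to 198 of 11,000 specimens would be excluded. The upper part of that range is incompatible with NPV also reaching 0.98: under both limits the ceilings are about 108, 76 and 22 at prevalences of 49%, 65.5% and 90%. The direction of the difference needs no assumption. Its size for a given category depends on the category's share and on how the misses are spread, neither of which the protocol gives. The primary analysis and the 0.98 criterion are unaffected.

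**What to change.** In section 6 of the protocol, and in the statistical analysis plan to match:

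- Define neoplastic sensitivity and urgent sensitivity on all specimens with that reference category, and count a COBix normal as a miss. State the denominator for specificity as well, and say what is meant by all abnormal cases.
- Report the full 5 × 5 cross-classification of reference against COBix category.
- Report the called-normal rate from the primary analysis by reference category, with exact 95% limits, above all for neoplastic urgent and non-neoplastic urgent.
- Keep the both-abnormal kappa, and any both-abnormal sensitivity, only as labelled conditional (second-stage) measures.

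The cost is wording and a little extra tabulation. Both classifications are already recorded for every specimen in the five categories, so no new data are needed. The reported secondary and tertiary sensitivities will be less favourable, and intervals for small categories will be wide.
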